### **Clinical Partner Sites:**

This study is being coordinated from a primary Research Coordinating Centre at Queen's University with 20 participating primary care sites (clusters) between Southeastern Ontario (14) and Interior British Columbia (6), Canada. Sites include representation from urban and rural settings in both regions to facilitate generalizability.

### **Patient and Public Involvement:**

A senior advisor for the Ontario Ministry of Health contributed to the plan for this study. An individual with lived experience is a co-author on this protocol (LC) who has been engaged in the design of this study, including the identification and decision on the trial outcome measures that are important to patients. Their involvement in carrying out the study includes pre-testing of data collection methods, interpretation of process evaluation results, and participation in the development of knowledge mobilization products (i.e., designing summaries appropriate for patient organizations).

### **Trial Interventions:**

#### **1. Index Intervention: PT-Led Primary Care Model for LBP**

The index intervention involves integrating a PT within the primary care team and making them available at the first point of contact for people with LBP. Patients with LBP are encouraged to book with the PT except when the primary reason for their visit is medication renewal or when additional health concerns require another provider's attention. The intervention has four components: 1) assessment and screening; 2) brief individualized intervention; 3) supporting patients to access appropriate health services based on assessment findings; and 4) providing additional PT care to people with an unmet need. Ten registered PTs, who have completed two days of training on this care model, are participating in delivery of the model across the 10 practices randomized to the PT-led primary care arm.

**Assessment and Screening:** The assessment and screening includes: taking a history; screening for pathology (e.g., cauda equina syndrome, traumatic fracture, cancer); physical and neurological examination; application of evidence-based tools to identify comorbid health conditions (e.g., 2-item Patient Health Questionnaire for depression) requiring additional care; and using a validated tool (Keele STarT Back Tool) to identify risk factors associated with persistent LBP and disability.

**Brief Individualized Intervention:** The PTs provide a brief individualized intervention at the initial visit. This intervention is intended to be based on primary care guidelines for LBP and consists of effective communication to validate the patient's experiences and allow the patient to disclose the impact of their LBP on their lives, cognitive reassurance, individually tailored exercises, and advice/strategies to stay active.

**Supporting Patients to Access Appropriate Health Services Based on Assessment Findings:** It is intended that the PT collaborates with the patient to identify appropriate health services based on assessment findings, collaborates with relevant primary care team members to provide the needed care, and integrates health service providers from outside of the team considering the patient's needs and access to health services. First, the PT identifies potential pathology needing urgent referral (e.g., cauda equina, fracture, infection). Next, they identify comorbid conditions that require collaboration with other primary care team members (e.g., physicians, nurse practitioners, nurses, social workers, occupational therapists, pharmacists, and dieticians). For example, people who screen positive for depression are referred to their physician or nurse practitioner or a member of the mental health team. Finally, primary care PTs refer to community PT as informed by the patient's score on the Keele STarT Back tool (if appropriate). The STarT Back tool categorizes patients with LBP into low, medium, or high risk of persistent pain and disability based on physical and psychosocial risk factors. The recommended matched treatment for low-risk patients is to provide self-management advice and to avoid referral and investigations where possible. This intervention is brief and it is expected that it can take place at the first visit. The recommended matched treatment for medium-risk patients is referral for standard community PT, and the matched treatment for high-risk patients is PT care from the primary care PT who received specific training aimed at reducing physical and psychosocial risk factors for chronic pain and disability as part of the two-day training. This stratified approach to care has demonstrated improved function, quality of life, and cost-effectiveness in comparison to usual care in the UK. When a need for PT care is identified, the primary care PT helps these patients navigate the available PT resources (i.e., private PT clinics when the patient has private health insurance; government funded PT for those who meet the criteria; or PT in primary care for those without access to a PT elsewhere).

**Providing Additional PT Care to People with an Unmet Need:** The PT provides additional care at the primary care site for patients who are appropriate for PT (based on STarT Back score) and who have barriers to accessing PT care in their community. For example, people who may benefit from physiotherapy but do not have access to services—due to a lack of private or government insurance coverage or because of geographic or transportation barriers—are offered additional physiotherapy care. Care includes evidence-based, guideline consistent management, such as individualized education exercise behavioural approaches. To avoid duplication of available PT services, patient participants with private or government funded health insurance for PT are referred to external PT services.

## **2. Comparison: Usual Physician-Led Care**

The usual physician- or nurse practitioner-led primary care intervention has been unstandardized to reflect usual primary care clinical practice in Canada. Our pilot study suggested the most common management approaches in the usual care model included: diagnostic imaging (12% of patients), medication renewal (21%), new medication prescription (14%), notes to employers (12%), and referral (PT 23%, chronic pain clinic 5%, massage therapy 5%, physician specialists 5%, and dietician 2%). Interventions provided or recommended by the physician have been and will continue to be recorded and monitored throughout the full trial.

There are no required or prohibited concomitant treatment options for either treatment arm. Should a participant choose to explore other or additional treatment options within their primary care team or from other health service providers, they are free to do so. This was made clear in the letter of information and consent form provided to the participants upon entry to the study.

### **Duration of Treatment Period:**

The PT-led primary care model is being implemented over a one-year period from the time of consent. All participants were offered an initial assessment with the PT and have access to the PT for follow-up needs for a one-year period after their initial assessment. The majority of participants classified as low-risk using the STarT Back tool and those with private or government-funded health insurance for PT are intended to only see the PT in primary care at their initial visit, but will have access to the PT as a member of their primary care team throughout the one-year follow-up period if they need or want a follow-up visit. Participants identified as medium or high risk without access to PT elsewhere are offered additional PT care from the PT in primary care. The frequency and duration of the treatment plan is determined by the PT and patient participant. In our pilot study, participants who took part in ongoing care received an average of four visits over eight weeks.

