### **Methods for Protecting Against Sources of Bias:**

Due to the trial design and interventions being compared, the PTs, patient participants, other members of the primary care team, and research assistants have not been blinded. While limitations due to the inability to blind are unavoidable, we have taken additional steps to minimize the risk of bias suggested for cluster trials. A common challenge in cluster trials is identification and recruitment bias when patient recruitment must take place after cluster allocation. To minimize the risks of these biases, we invited consecutive patients to participate, provided the same information about the trial to both groups prior to participants consenting (not revealing the cluster allocation until after consent and baseline data collection), employed research assistants unfamiliar with the patients to recruit and consent participants, and rigorously applied inclusion/exclusion criteria at all sites.

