### **Frequency and Duration of Follow-Up:**

Patient characteristics and demographic information were collected at baseline. All patient-reported outcome measures are being collected at baseline, 6 weeks, and 3, 6, 9, and 12 months from the initial visit, with the primary comparison at 12 months. Patient satisfaction, global rating of change, adverse effects, and healthcare utilization are being collected at follow-up time points only. Patient adherence to PT recommendations is being collected at the 6-week follow-up.

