### **Implementation Measures:**

The following measures will be used to assess how the PT-led primary care model and usual physician- or nurse practitioner-led primary care model were implemented.

**Timely access to LBP care:** using the percentage of patient participants with LBP who are assessed within 48 hours of calling for an appointment. Participants who learned about the study and were invited to participate during an appointment for their LBP will not be included in this analysis.

**PT as the first point of contact:** using the percentage of patient participants with LBP in the PT-led primary care arm who visited a PT as their first point of contact for the current episode of LBP.

**Access to PT services:** using the percentage of patients who are classified as medium or high risk on the STarT Back screening tool who access PT (as endorsed by guidelines).

**LBP management:** using the following data being collected from the EHR to describe the LBP management provided to patient participants in each arm: education; exercise; psychological approaches; referrals to other primary care team members (e.g., primary care physicians, nurse practitioners, nurses, social workers, occupational therapists, group programming); referrals made to health professionals outside of the primary care team; medications prescribed, deprescribed, and suggested; diagnostic imaging ordered; lab work ordered and received; notes to employers or insurers; interprofessional communications with the primary care team; and other interventions provided.

**Patient adherence to recommendations:** adherence to recommendations from the primary care PT is being collected at the 6-week follow-up. For patient participants identified as medium- or high-risk using the STarT Back classification, whether or not they accessed recommended PT (either through a referral to a community PT or through the PT in primary care) is being collected as part of our health utilization survey questions.

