### Process evaluation analysis

The multi-methods process evaluation analysis will assess how the PT-led primary care model for LBP was implemented, the potential mechanisms of the model, the experiences and perspectives of patients and primary care team members toward the model, and how the context influenced implementation and outcomes. The analysis is guided by and intended to inform refinements to our program theory for the PT-led primary care model program for LBP (**Figure 1**).

We will assess how the PT-led primary care model and usual care model were implemented and how the model influenced healthcare for people with LBP by:

- 1) Describing and comparing the proportion of patient participants who received timely access to LBP care between trial arms. The intended implementation outcome is that patient participants seeking primary care for LBP receive timely access (within 48 hours) to a LBP assessment from a PT in the PT-led primary care model for LBP. Access within 48 hours will be presented as incidence rates with confidence intervals and compared by calculating relative risks with confidence intervals using GEE-type variance estimators to account for clustering, using an exchangeable working correlation matrix. We will use empirical covariance (“sandwich”) bias-adjusted (residual-based) estimators and the Fay and Graubard correction to account for small number of clusters. We will incorporate the same covariates as with our effectiveness analysis.
- 2) Describing the proportion of patient participants in the PT-led primary care arm who saw the PT as the first point of contact for the current episode of LBP.

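### Follow-up is timed from an undefined initial visit while other sections start at baseline or consent, so survey timing may differ by arm and events during the wait may go uncounted

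*Combined protocol and SAP*

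**What the plan says.** The combined protocol and SAP uses several starting points.

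- **Table 1 (Trial Design)** places time 0 at baseline, in the column for enrolment of patient participants. The 6-week to 12-month columns sit on the same axis.
- **Duration of Treatment Period** says "The PT-led primary care model is being implemented over a one-year period from the time of consent". The next sentence says participants "have access to the PT for follow-up needs for a one-year period after their initial assessment".
- **Frequency and Duration of Follow-Up** says "All patient-reported outcome measures are being collected at baseline, 6 weeks, and 3, 6, 9, and 12 months from the initial visit".

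The term initial visit is not defined. The description of the index intervention uses it for the first clinical contact: "The PTs provide a brief individualized intervention at the initial visit". Duration of Treatment Period uses it the same way. No equivalent visit is described for usual care.

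Baseline is collected close to consent, with the team "not revealing the cluster allocation until after consent and baseline data collection". Under Recruitment there are two routes into the trial. Some patients were identified when booking an appointment. Others had already raised back pain with a provider during an encounter.

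Time to first assessment is itself a target of the model. Implementation Measures records the share of participants "assessed within 48 hours of calling for an appointment". The process evaluation intends that patients "receive timely access (within 48 hours) to a LBP assessment from a PT in the PT-led primary care model for LBP" and compares this access measure between arms.

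**The concern.** A follow-up clock should start at a point the intervention cannot move. If initial visit means the first clinical visit, this clock starts after allocation, at an event whose timing the PT-led model is designed to change. Two consequences could follow.

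1. The arm that waits longer is surveyed later after baseline, so it has had more time for natural recovery at each nominal time point. This matters most at 6 weeks and 3 months, when scores may still be changing quickly.
2. Days lost, visits, costs and utility during the wait may fall before the clock starts. Shorter waiting is one of the benefits the model aims for, so leaving the wait out of the one-year totals could hide part of the effect.

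The analysis text does not settle the matter. The primary model uses the scheduled time points and mentions no actual survey dates. The utilization models use a time offset whose origin is not stated. The economic section names the follow-up assessments as its source of utilities and does not mention baseline. No survey window or recall period is given.

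**Working it through.** **The plan's own figure.** Sample Size and Power Calculations states 90% power with 18 clusters of 63, difference 2.5, SD 5.7, ICC 0.1, cluster autocorrelation 0.5 and individual autocorrelation 0.6.

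- Design effect before baseline adjustment: 1 + 62 × 0.1 = 7.2.
- Baseline to follow-up correlation of cluster means: (63 × 0.1 × 0.5 + 0.9 × 0.6) / 7.2 = 0.5125.
- SE = √[2 × 5.7² × 7.2 × (1 − 0.5125²) / (63 × 9)] = 0.780.
- Power = Φ(2.5 / 0.780 − 1.96) = 0.893.

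The stated figure reproduces on the normal approximation, and it does not depend on where the clock starts.

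**Shift in survey day.** If a survey is due *d* days after the first visit and the visit is *w* days after baseline, the survey falls on day *d* + *w*. The values of *w* are assumptions.

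- *w* = 2: 6-week survey on day 44, 12-month survey on day 367.
- *w* = 7: days 49 and 372.
- *w* = 14: days 56 and 379.
- *w* = 21: days 63 and 386.

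A 14-day wait lengthens the 6-week interval by 14/42 = 33% and the 12-month interval by 14/365 = 3.8%. It takes 14/365 = 0.038 years out of a one-year QALY or cost window, or adds it.

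**Spurious contrast with no treatment effect.** Assume that both arms recover identically from consent. The mean RMDQ excess *t* weeks after consent is *D* × 0.5^(*t*/*h*), with total drop *D* = 4 or 6 points and half-life *h* = 3, 6 or 10 weeks. Assume a first visit at 2 days in the PT-led arm and at 7, 14 or 21 days in usual care. At nominal week *k* the artefact is

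*D* × 0.5^((*k* + 2/7)/*h*) − *D* × 0.5^((*k* + *w*/7)/*h*).

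- *k* = 6: 0.12 to 0.78 points. The maximum is at *D* = 6, *h* = 6, *w* = 21, and 0.78 / 2.5 = 31% of the target difference.
- *k* = 13: 0.03 to 0.41 points.
- *k* = 52: under 0.03 points.

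Under these assumptions the artefact runs against PT-led care. Reducing a true 12-month difference of 2.5 by 0.03 gives power Φ(2.47 / 0.780 − 1.96) = 0.886 against 0.893.

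**Days lost before the clock.** If 10% to 30% of waiting days are days of missed activity (assumed), the difference between arms is (*w* − 2) × 0.1 to 0.3. This runs from 5 × 0.1 = 0.5 to 19 × 0.3 = 5.7 days per participant.

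**Direction.** For a patient recruited during an encounter, the back pain visit comes before consent. If that encounter counts as the initial visit, the offset is zero or negative. If the later PT assessment counts instead, the PT-led arm has the later clock and the sign above could reverse. The documents give no split between the two routes.

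**The case against.** The strongest reply is that this is loose wording. Table 1 puts baseline and all follow-ups on one axis, and the follow-up section lists baseline as the first point of its series, so initial visit may simply mean the baseline contact. The two clocks under Duration of Treatment Period concern delivery of the model and access to the PT, not survey timing. Faster access is measured directly, from the call, and compared between arms. The baseline EQ-5D-5L could bring the wait into the area under the curve, and record data could cover it. Every input to the sizes above is assumed. The 2-day figure treats an intended target, counted from the call, as an achieved wait counted from consent. Patients with back pain of any duration are eligible, so rapid average recovery cannot be presumed.

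Much of this stands, and it rules out three stronger readings that a reader might infer.

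- *Surveys do fall at different times by arm.* This needs both the clinical meaning of initial visit and unequal waits, and the documents establish neither.
- *The benefit of faster access is removed from costs and QALYs.* With no recall period, extraction window or QALY start date stated, the wait may or may not be counted.
- *Participants who never attend drop out, in breach of intention-to-treat.* Nothing says they receive no surveys. Data Collection and Management says that each participant is sent a link at each time point, and the analysis section commits to intention-to-treat.

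The reply does not remove the conflict. Where the document shows what initial visit means, it means a clinical visit, and the survey section uses that term as its anchor.

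**Conclusion.** The concern holds as an unresolved conflict in time zero that could bias secondary results. It is not a demonstrated bias. It depends on initial visit meaning the first clinical visit and on waits that differ by arm. The documents support the first by usage only and are silent on the second. Because some patients were seen before consent, neither the size nor the direction can be stated.

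A reader might also infer a threat to the primary result. On the assumptions shown, the 12-month RMDQ contrast moves by under 0.03 points, so that inference is not supported. The outcomes at risk are the 6-week and 3-month contrasts and the one-year totals for missed work, utilization, costs and QALYs. The change should be made, and since analysis starts only after data collection ends, the rule can still be fixed in advance.

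**What to change.** 1. Reconcile Table 1, Duration of Treatment Period and Frequency and Duration of Follow-Up, and define initial visit for both arms. The two statements about the PT-led year must be made consistent; which one applies to access is for the investigators. If surveys were in fact sent from baseline, correcting the follow-up section settles the survey clock.
2. Make consent/baseline the single analysis time zero in both arms, including for participants who never attend a first visit.
3. Use actual days from consent to each survey in the QALY area under the curve, starting from the baseline EQ-5D-5L, and in a sensitivity analysis of the early RMDQ contrasts.
4. Run the window for EHR counts, costs and the utilization offset from consent to day 365 for everyone.
5. State survey recall periods and windows, and report by arm the days from baseline to first visit and to each survey.

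Relabelling surveys to the nearest nominal time point would achieve little. With a wait of up to 21 days, the 6-week survey falls no later than day 63, the midpoint of days 42 and 84, so almost none would change label.

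The cost is some extra programming, provided consent and survey dates were recorded. The extraction window shifts by the length of the wait. For participants recruited during an encounter, the index visit before consent is excluded, which bears on the physician-visit outcome. Self-reported days lost during the wait cannot be recovered if the surveys did not ask about them, and the report should say so.

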### **Intervention Modifications:**

We do not anticipate encountering a situation that would require the withdrawal of a participant for safety concerns related to the PT-led primary care or usual physician-led primary care. As per normal primary care and PT practice for LBP, the intervention will be modified by the primary care team to maintain participant safety as part of the model of care (e.g., modification of exercise in response to increases in pain that may be experienced with an exercise intervention, discontinuation of medications if adverse effects are experienced). Due to the low-risk nature of the study and the fact that patient participants maintained access to their usual primary care providers, a Data Monitoring Committee was not established. Ongoing oversight and patient participant safety monitoring was provided by the study investigators, including monitoring all adverse events reported at all time points.

### **Data Collection and Management:**

All patient participant-reported outcome measures are being collected from participants using REDCap (Research Electronic Data Capture), a secure online survey and data capture tool hosted at Queen's University. A distinct link for the surveys is being sent to each participant at each assessment time-point. We are providing the option of completing the questionnaires in-person or by phone if participants have barriers to completing them online. Data are also being extracted from participants' electronic health records (EHR) related to care provided for LBP. Data are being extracted using pre-piloted EHR extraction forms.

At study completion, responses to the surveys will be exported directly from REDCap to encrypted and password protected datasets and stored securely in Microsoft OneDrive at Queen's University. All data collected from the EHR, along with a master linking log that links study identification numbers with participants, will be stored in password-protected and encrypted files in OneDrive. The linking log will be permanently destroyed at the end of the data analysis period. Qualitative interview recordings will be transcribed, deidentified, and stored securely in OneDrive.

We implemented multiple strategies to promote participant retention across all time points. Research assistants sent reminders every 2-3 days through personalized emails, phone calls, and text messages to encourage timely survey completion. When requested, surveys were completed in-person or by phone to strengthen engagement and minimize loss to follow-up.

